##### **3.1.1 Dose Limiting Toxicity (DLT)**

A DLT will be defined as any Grade 3 or higher toxicity that occurs during the initial 6-week period the subject is on treatment (i.e., the DLT evaluation period). Toxicity that is clearly and directly related to the primary disease or to another etiology is excluded from this definition. Since this trial also involves immunotherapy, immune-related AEs (irAEs) are defined as AEs of an immune nature (i.e. inflammatory) in the absence of a clear alternative etiology. In the absence of a clinically significant abnormality, repeat laboratory testing will be conducted to confirm significant laboratory findings prior to designation as a DLT. The following will be DLTs:

- Inability to reduce prednisone dose below 10 mg within 6 weeks (rather than 12 weeks) due to ongoing immune-related adverse reaction of Grade >1
- Any Grade 4 irAE not attributed to local tumor response (e.g., inflammatory reaction attributed to local tumor response or inflammatory reaction at sites of metastatic disease or lymph nodes)
- Any  $\geq$  Grade 3 colitis
- Any Grade encephalopathy
- Any  $\geq$  Grade 3 neurotoxicity
- Any  $\geq$  Grade 3 peripheral neuromotor syndromes
- Any Grade 2 or higher noninfectious pneumonitis irrespective of duration
- Any Grade 3 irAE, excluding colitis that does not downgrade to Grade 2 within 3 days after onset of the event despite optimal medical management including systemic corticosteroids or does not downgrade to  $\leq$  Grade 1 or baseline within 14 days

- Total bilirubin  $>1.5 - 3.0 \times$  ULN (Grade 2 Hyperbilirubinemia)
- ALT or AST  $>8 \times$  ULN
- ALT or AST  $>5 \times$  ULN for more than 2 weeks
- ALT or AST  $>3 \times$  ULN and
- ALT or AST  $>3 \times$  ULN and INR  $>1.5$
- ALT or AST  $>3 \times$  ULN with appearance of fatigue, nausea, vomiting, right upper quadrant pain or tenderness, fever, rash, and/or eosinophilia ( $>5\%$ )
- Any Grade  $\geq 3$  non-irAE toxicity that does not downgrade to Grade  $\leq 1$  or baseline status (for patients who entered the study with an existing laboratory abnormality) within 14 days
- Inability to receive  $\geq 75\%$  or more of scheduled study treatment (both Vicineum and durvalumab) during the first six weeks of the trial

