#### **3.2.1.2 Monitoring of dose administration**

Subjects will be monitored before, during and after the infusion with assessment of vital signs at the times specified in the Schedule of Assessment. Subjects are monitored (pulse rate, blood pressure) every 30 minutes during the infusion period (including times where infusion rate is slowed or temporarily stopped).

In the event of a  $\leq$ Grade 2 infusion-related reaction, the infusion rate of study drug may be decreased by 50% or interrupted until resolution of the event (up to 4 hours) and re-initiated at 50% of the initial rate until completion of the infusion. For subjects with a  $\leq$ Grade 2 infusion-related reaction, subsequent infusions may be administered at 50% of the initial rate. Acetaminophen and/or an antihistamine (e.g., diphenhydramine) or equivalent medications per institutional standard may be administered at the discretion of the investigator. If the infusion-related reaction is Grade 3 or higher in severity, study drug will be discontinued. The standard infusion time is one hour, however if there are interruptions during infusion, the total allowed time from infusion start to completion of infusion should not exceed 4 hours at room temperature, with maximum total time at room temperature not exceeding 4 hours (otherwise requires new infusion preparation).

As with any antibody, allergic reactions to dose administration are possible. Appropriate drugs and medical equipment to treat acute anaphylactic reactions must be immediately available, and study personnel must be trained to recognize and treat anaphylaxis. The study site must have immediate access to emergency resuscitation teams and equipment in addition to the ability to admit subjects to an intensive care unit if necessary.

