### 3.3.2 Vicineum

Following any biopsy or TURBT, study drug must be interrupted for a minimum of 1 week and maximum of 2 weeks before restarting Vicineum treatment. Patients who develop low grade papillary disease will be allowed to stay on trial. In November 2016, the FDA published a draft guidance for trials involving patients with BCG-unresponsive disease in which only high-risk disease counts as a recurrence or an event. In this clinical setting, low-risk disease would lead to transurethral resection while high-risk disease would lead to cystectomy, which is a much different clinical outcome. Therefore, in this trial, low grade recurrences will be documented but will not count as a trial-ending recurrence or event. Furthermore, low grade recurrences are considered to be downstaging of disease since the inclusion criteria requires patients with high grade disease.

Study drug administration must be postponed if a subject develops any Grade 3 or greater adverse event. Study treatment may resume when the AE returns to  $\leq$  Grade 1 or baseline or sooner if there is agreement between the investigator and the sponsor. Study treatment may be postponed at the discretion of the investigator for unrelated AEs, if this is considered in the best interest of the subject. If the causal relationship between Vicineum and an AE is initially uncertain, study drug should be interrupted until that determination is made. Also study treatment may be postponed for lower grade AEs at the investigator discretion if considered in the best interest of the subject.

The following specific criteria will be used for holding Vicineum dosing based on serum creatinine and calculation of creatinine clearance:

Baseline Creatinine	Criteria for Holding Vicineum Treatment*	
	Serum Creatinine	Creatinine Clearance
<1.0 mg/dl or <88 $\mu$ mol/L	>1.5 mg/dl or >133 $\mu$ mol/L	<40 ml/min or a decrease of 25% from baseline
$\geq$ 1.0 mg/dl or $\geq$ 88 $\mu$ mol/L	Increase to $>2 \times$ Baseline Value	<40 ml/min or a decrease of 25% from baseline

\*Vicineum dosing should be held if either the serum creatinine or the creatinine clearance criteria, as defined in this table, are met.

If changes in renal function are noted, the investigator should evaluate the subject for the etiology of these changes. Vicineum treatment may be resumed upon improvement or stabilization at creatinine of  $\leq 2 \times$  baseline or  $\leq 2 \times$  ULN.

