Tumor CT/CT urogram or MRI/MRI urogram of abdomen and pelvis 	X							Every 12 months while on study

SCHEDULE OF STUDY ASSESSMENTS: Screening (Weeks -12 to -1), Induction Phase (Weeks 1 – 12), and Post-Induction Evaluation (All assessments can be performed within +/- 7 days of scheduled assessment to accommodate holidays and scheduling difficulties)									
Assessments to be performed at the times stipulated in the table and as clinically required in the management of the subject  .	Screening	Baseline	All assessments to be performed pre-infusion unless stated otherwise						Post-Induction and Maintenance
			Week 1	Weeks 2 - 5	Week 6	Weeks 7 - 11	Week 12		
Day	-84 to -1	-7 to 0							
Week	-12 to -1	-1							
Urinary PK for Vicineum		X	X 	X 					
Urinary EpCAM levels		X	X 	X 	X (before Vicineum)	Week 10 (before Vicineum)	X (before Vicineum)		
Follow-up Safety Visits for patients who come off treatment or complete study 								Every month up to 90 days post the last dose of immunotherapy 	

1. May be performed up to 12 weeks prior to enrollment.
2. Pre-menopausal female subjects of childbearing potential only.
3. Dose can be administered within +/- 7 days of scheduled administration to accommodate schedule and holidays.
4. Once weekly intravesical administration for weeks 1-12; Dose can be administered within +/- 7 days of scheduled administration to accommodate schedule and holidays.
5. Full physical examination at screening and/or baseline; targeted physical examination at other timepoints and when clinically indicated.

6. Vital signs will be obtained at a single timepoint at screening and baseline. Subjects will have their blood pressure and pulse measured before, during and after the infusion at the following times (based on a 60-minute infusion):
  - At the beginning of the infusion (at 0 minutes)
  - At 30 minutes during the infusion ( $\pm 5$  minutes)
  - At the end of the infusion (at 60 minutes  $\pm 5$  minutes)
  - In the 1 hour observation period post-infusion: 30 and 60 minutes after the infusion (ie, 90 and 120 minutes from the start of the infusion) ( $\pm 5$  minutes) – for the first infusion only and then for subsequent infusions as clinically indicated.

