### **3.6.1 Criteria for Removal from Protocol Therapy**

Subjects are free to withdraw from further treatment or to withdraw consent to participate in this study at any time and without prejudice to further treatment. For subjects who withdraw their consent for study participation, no further study specific assessments will be performed and no additional study data will be collected. For subjects who withdraw from further treatment only will remain on study for further evaluations but receive no additional study treatment. The investigator may also withdraw a subject from study treatment or from the study if he or she deems it to be in the best interest of the subject or if the subject is unable to comply with the study. All subjects withdrawing only from further treatment should have enter the Post-Treatment Period and have the appropriate assessments performed 90 days after the last dose of study drug, unless the subject withdraws consent for the procedures. If clinically indicated, patients may continue to be followed by phone or clinic visits beyond that time and up to a year at the NIH/NCI or their local urologist. The reasons and details relevant to subject withdrawal must be recorded in the source documents and in the CRFs.

In addition, an individual subject will not receive any further investigational product if any of the following occur in the subject in question:

- Completion of protocol therapy

- Unacceptable toxicity as defined in section [3.3](#) and [Appendix C](#)
- Adverse event that, in the opinion of the investigator, contraindicates further dosing of either study drug
- Subject experiences a DLT during the DLT evaluation period (see section [3.1.1](#))
- Requirement for prohibited medications/therapies
- Subject met eligibility criteria at screening but then subsequently is determined to have met one or more of the exclusion criteria for study participation and continuing investigational therapy might constitute a safety risk
- Subjects refuses to use contraception as required by the protocol
- Disease progression (as defined in section [6.2.4.3](#)) or confirmation that the subject is no longer benefiting from study treatment
- Grade 2 or greater hyperbilirubinemia
- Participant requests to be withdrawn from active therapy
- Unacceptable Toxicity as defined as any serious adverse event that is unexpected relative to the known safety profile of the investigational agents in the opinion of the investigator

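### Section 3.1.1 defines a dose-limiting toxicity in two conflicting ways without saying which governs, so the same six patients can pass or fail the 3+3; the primary endpoint in 10.1 is also not worded in terms of DLTs

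*Combined protocol and SAP*

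**What the plan says.** **Opening sentence of 3.1.1.** "A DLT will be defined as any Grade 3 or higher toxicity that occurs during the initial 6-week period the subject is on treatment". Toxicity clearly caused by the disease or by something else is left out. There is no condition on duration or reversibility.

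**List in 3.1.1.** Introduced as the events that will be DLTs, it includes a Grade 3 or higher "non-irAE toxicity that does not downgrade to Grade" 1 or baseline within 14 days. It includes Grade 3 immune-related events other than colitis if they fail to reach Grade 2 in 3 days, or Grade 1 or baseline in 14 days. Some events count outright (for example Grade 3 or higher colitis or neurotoxicity). Some lie below Grade 3: Grade 2 pneumonitis, Grade 2 bilirubin, encephalopathy of any grade, persistent Grade 2 events. Two further items are "Inability to reduce prednisone dose below 10 mg within 6 weeks" because of an ongoing immune reaction, and inability to receive at least 75% "or more of scheduled study treatment (both Vicineum and durvalumab) during the first six weeks of the trial".

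**Exclusions in 3.1.1.** There are five. They include a first Grade 3 infusion reaction settling within 6 hours and isolated Grade 3 electrolyte changes reversed within 3 days. None covers transient Grade 3 events in general.

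**Consequences.** Sections 3.1.2 and 10.2 use the DLT count for de-escalation, for expansion and for the rule that the cumulative fraction stay below 1/3. Section 10.4.2 sets the MTD at 0 or 1 DLT in 6. Section 3.6.1 ends treatment when "Subject experiences a DLT during the DLT evaluation period". Section 3.3.2 says "Study drug administration must be postponed if a subject develops any Grade 3 or greater adverse event" and lets treatment resume on recovery.

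**Primary endpoint.** Section 10.1 names the fraction of patients with adverse events, with no grade, attribution, window or threshold. The sentence before it says that safety is judged by the 3+3.

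**The concern.** A related Grade 3 event that settles in a week is a DLT under the opening sentence and, unless the list counts it outright, is not a DLT under the list. Neither text can be set aside as loose drafting. If the opening sentence governs, the 3-day and 14-day conditions do nothing. If the list governs, exclusions such as the 6-hour infusion reaction are largely redundant, because the list would not normally catch those events.

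The DLT count is the only quantity that drives the dose decision, and it also decides whether an individual patient stops treatment. Two careful readers could report different MTDs from the same data. The endpoint sentence in 10.1 adds a mismatch between what is called primary and what decides the question.

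**Working it through.** **The plan's own figure.** The plan states no operating characteristics for the 3+3 or for the primary endpoint. The only power figure tied to 24 patients is 90% for the biomarker comparisons in 10.2. A paired t-test with n = 24, effect size 1.0, two-sided alpha 0.05/25 = 0.002, 23 df and noncentrality √24 gives 90.2%. The figure reproduces and does not depend on this point.

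**Worked cases.**
- Two of six patients have a related, non-immune Grade 3 event that is back to Grade 1 within 14 days, is not on the exclusion list, and leaves at least 75% of treatment given. The opening sentence gives 2/6, so the level fails. The list gives 0/6, so the level passes and 18 more are enrolled.
- Two of six have Grade 2 pneumonitis. The opening sentence alone gives 0/6; the list gives 2/6.

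So neither definition contains the other.

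**Size.** Under 10.2 a level passes with 0/6 or 1/6. With DLT probability p:

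P(pass) = P(0/3)·P(≤1/3) + P(1/3)·P(0/3) = (1−p)^6 + 6p(1−p)^5.

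Let pL be the DLT rate under the list and t the added rate of transient Grade 3 events that count only under the opening sentence. Both are assumptions. Leaving aside Grade 2 list-only events, every list DLT is also an opening-sentence DLT. The chance that the two readings disagree is then P(pass at pL) − P(pass at pL + t). Each cell gives the pass probability under the opening sentence, with the disagreement in brackets.

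| pL | Pass under list | t = 5% | t = 10% | t = 15% | t = 20% |
|---|---|---|---|---|---|
| 5% | 96.7% | 88.6% (8.1) | 77.6% (19.1) | 65.5% (31.2) | 53.4% (43.3) |
| 10% | 88.6% | 77.6% (10.9) | 65.5% (23.0) | 53.4% (35.2) | 42.0% (46.6) |
| 15% | 77.6% | 65.5% (12.1) | 53.4% (24.3) | 42.0% (35.6) | 31.9% (45.7) |

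The disagreement runs from about 8% to 47%. In expansion the same ambiguity bears on the 1/3 limit: 7/24 = 29.2% continues and 8/24 = 33.3% does not.

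**The 75% item.** Weeks 1-6 hold six weekly Vicineum doses and two durvalumab doses (weeks 2 and 6). One durvalumab dose not given is 1/2 = 50% counted per drug, which fails, and 7/8 = 87.5% pooled, which passes. The text does not say which count applies. It also does not say how the item relates to the calendar footnote, "Dose can be administered within +/- 7 days of scheduled administration to accommodate schedule and holidays", or to the excluded infusion reaction, for which 3.2.1.2 says "If the infusion-related reaction is Grade 3 or higher in severity, study drug will be discontinued".

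**Timing.** The window ends at day 42. A 14-day resolution period that starts after day 28 ends beyond it. Durvalumab starts in week 2 (day 8 at the earliest), so six weeks of steroid for a durvalumab reaction ends no earlier than day 8 + 42 = day 50.

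**The case against.** The strongest reply is that specific text governs general text. Section 3.3.2 applies a list item (Grade 2 bilirubin) as a DLT. Appendix C says the protocol-specific DLTs of 3.1.1 override it and names toxicities that appear in the list. This shows that the list is operative. It does not show that the opening sentence is not: a reader could apply both and subtract the exclusions, which empties the 3-day and 14-day conditions. The conflict stands.

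Several stronger inferences are tempting and are not supported:

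- *That 3.3.2 and 3.6.1 contradict each other independently.* Section 3.3.2 covers the whole course, and its bilirubin rule shows a DLT overriding hold-and-resume inside the window. Once 3.1.1 is settled, the two can be read together.
- *That a week-6 durvalumab dose given in week 7 breaches the 75% item.* That assumes per-drug counting and treats permitted rescheduling as inability. Likewise, the exclusions follow the whole list and may be read as covering every item, so an excluded infusion reaction need not re-enter as a DLT.
- *That the steroid item can never be judged in time.* Section 3.1.2 takes the decision once the whole cohort has passed the window, on all available safety data. At the one patient per month of 10.2, the first two of three patients would be roughly 14 and 10 weeks in. The gap concerns late-onset events and the last-enrolled patient.
- *That the primary question has no answer, or that the adverse-event fraction will be near 100%.* Sections 10.1 and 10.4.2 tie the decision to DLTs, 10.4.1 reports the fraction with toxicity by dose level, and 10.4.2 also tabulates all toxicities. Dysuria was 60.9% in the Phase 2 trial regardless of cause, but any Vicineum-related event was 50% in Phase 3.
- *That 88.6% against 42.0% is the expected size.* It is the top of the range and needs a 30% rate that the documents do not support. Related Grade 3 or higher events were 10.0% in the pooled durvalumab data. Related Grade 3 events were 4.9% in the urothelial cohort, with none higher. Vicineum-related events of Grade 3 or higher were about 4% in Phase 3. All are single-agent rates over whole exposure.

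It is also true that much of the harm is now retrospective: 1.2.3 already reports 12-week results in 12 patients. That changes the remedy and leaves the defect in place.

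**Conclusion.** The point holds for 3.1.1: two conflicting DLT definitions stand in one section, nothing ranks them, and the choice can reverse the dose decision and an individual patient's removal. Over the assumed rates the readings disagree with probability about 8-47%. Examples are 96.7% against 88.6% at 5% and 10%, and 88.6% against 42.0% at 10% and 30%. The calculation assumes independent patients and ignores Grade 2 list-only DLTs, which act in the opposite direction. The documents give no six-week rate for the combination, so no single value in the range can be called the effect.

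The 75% count and the timing of late criteria are secondary ambiguities. The 10.1 wording is a mismatch between endpoint and decision variable; it does not itself change the 3+3 result.

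**What to change.** - Reconcile the opening sentence, list and exclusions of 3.1.1 into one governing rule. Which rule is a clinical decision for the sponsor, and this review does not choose.
- Make 3.3.2 and 3.6.1 consistent with that rule.
- State whether the 75% item is counted per drug or pooled, and how it relates to the 7-day dosing window and the infusion-reaction exclusion.
- State when the 14-day and six-week steroid items are adjudicated relative to the cohort decision.
- For patients already treated, tabulate DLTs by dose level under both readings, so that any effect on the dose decision is visible.
- In 10.1, state the primary endpoint as the proportion of treated patients with a DLT in the first 6 weeks at each dose level, with an exact 95% confidence interval, matching 10.4.2. Give all adverse events by grade as supporting.

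The cost is wording in 3.1.1, 3.3.2, 3.6.1 and 10.1 and one extra safety table. No patients or procedures are added.

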- Persistent Grade 2 events possibly related to study drugs such as persistent nausea, vomiting, diarrhea, or fatigue that are refractory to maximal intervention or are severely limiting to the patient's ability to carry out activities of daily living.

The definition excludes the following conditions:

- Grade 3 endocrine disorder (thyroid, pituitary, and/or adrenal insufficiency) that is managed with or without systemic corticosteroid therapy and/or hormone replacement therapy and the subject is asymptomatic
- Concurrent vitiligo or alopecia of any AE grade
- Grade 3 infusion-related reaction (first occurrence and in the absence of steroid prophylaxis) that resolves within 6 hours with appropriate clinical management
- Isolated Grade 3 electrolyte abnormalities that are not associated with clinical signs or symptoms and are reversed with appropriate maximal medical intervention within 3 days.
- Grade 3 inflammatory reaction attributed to a local antitumor response (e.g., inflammatory reaction at sites of metastatic disease, lymph nodes, etc.)

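### Section 3.1.1 gives two DLT rules that disagree on some brief, treatment-related Grade 3 events, and no text says which governs

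*Combined protocol and SAP*

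**What the plan says.** Section 3.1.1 defines a DLT in three steps.

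- **Opening rule.** "A DLT will be defined as any Grade 3 or higher toxicity that occurs during the initial 6-week period the subject is on treatment". Toxicity clearly due to the disease or another cause is removed. Duration is not mentioned.
- **List of DLTs.** Some entries carry time limits. One is Grade 3 or higher "non-irAE toxicity that does not downgrade to Grade" 1 or below, or to baseline, within 14 days. Another reads "Any Grade 3 irAE, excluding colitis that does not downgrade to Grade 2 within 3 days after onset of the event", or that does not reach Grade 1 or baseline within 14 days. ALT or AST above 5 times "ULN for more than 2 weeks" is a third. Other entries have no such limit: Grade 3 colitis, neurotoxicity and neuromotor syndromes, noninfectious pneumonitis from Grade 2, ALT/AST above 8 x ULN, and ALT/AST above 3 x ULN with INR above 1.5 or with symptoms. Failure to receive at least 75% of scheduled treatment in the first six weeks is also a DLT.
- **Exclusions.** These include symptom-free isolated Grade 3 electrolyte changes that "are reversed with appropriate maximal medical intervention within 3 days" and a first Grade 3 infusion reaction that "resolves within 6 hours with appropriate clinical management".

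Section 3.6.1 stops all investigational product after a DLT in the window. Section 3.3.2 says: "Study drug administration must be postponed if a subject develops any Grade 3 or greater adverse event". It continues: "Study treatment may resume when the AE returns to" Grade 1 or below, or baseline. Section 10.4.2 reports DLTs per dose level and sets the MTD at 0 or 1 DLT in 6. Sections 3.1.2 and 10.2 require the cumulative DLT fraction to stay below one third.

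**The concern.** The opening rule has no time limit, while the list makes time to recovery decisive for most Grade 3 events. No wording presents the list as an addition to the opening rule or as a replacement for it. Two careful readers could therefore give the same patient different DLT status.

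That status feeds the DLT table and the MTD statement, counts toward the one-third rule, and determines whether the patient continues treatment. If the rule is settled only when the table is drawn up, the choice is made with the events already known.

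**Working it through.** The plan states no operating characteristic for the DLT definition, so there is no figure to reproduce. The check is a comparison of the rules, followed by an illustration of size.

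**Step 1. Dosing in the first six weeks (Section 3.4).** Vicineum is given in weeks 1 to 6 (6 doses) and durvalumab in weeks 2 and 6 (2 doses). Section 3.3.2 says missed Vicineum doses are not made up.

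**Step 2. Test cases.**

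*Case A, non-immune.* A related Grade 3 event starts two days after the week-3 instillation and is at Grade 1 eight days later. It is in no named category and on no exclusion. Only the week-4 Vicineum dose is lost: 5/6 = 83% for Vicineum, 2/2 for durvalumab and 7/8 = 87.5% pooled, so the 75% entry is not met.
- Opening rule: DLT.
- List: not a DLT, because it resolved within 14 days.

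*Case B, immune.* A Grade 3 immune rash starts two days after the week-6 doses, is Grade 2 on day 2 and Grade 1 on day 10. All 6 + 2 doses were given.
- Opening rule: DLT.
- List: not a DLT, because both limits were met.

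*Case C, transaminase.* ALT is 6 x ULN, falls below 3 x ULN by day 3 and is normal by day 14, with normal bilirubin and INR, no symptoms or eosinophilia, and dosing at or above 75%.
- Opening rule: DLT only if 6 x ULN is Grade 3. This is an assumption, because the protocol does not print the cut-off.
- List: not a DLT by any complete entry. (One ALT/AST entry breaks off after its first condition and is not used here.)

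Cases A and B need no outside figure.

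**Step 3. What each reading does to the text.** If the opening rule governs, the 3-day, 14-day and 2-week limits do not change the classification of any Grade 3 event. If the list governs, the phrase about any Grade 3 toxicity is wrong as written, and the electrolyte exclusion is largely redundant because the 14-day entry already leaves those events out.

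**Step 4. Consequence at the threshold.** With one DLT already among six, a patient like Case A makes 2 of 6 under the opening rule and leaves 1 of 6 under the list. The MTD criterion is met only in the second.

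**Step 5. Illustrative size.** The 6-week rate is not given. As an upper guide, single-agent rates over all follow-up are:
- durvalumab-related Grade 3 or higher, 164/1645 = 10.0% (Section 1.2.1.2);
- Vicineum-related Grade 3 to 5, (4 + 1)/133 = 3.8% (Section 14.2.2.3, Table 3; N of about 133 inferred from 66 patients being 50%).

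Without overlap they sum to 13.7%. Assume that half of such events are brief enough to escape the list. With p the DLT probability per patient, P(2 or more of 6) = 1 − [(1−p)^6 + 6p(1−p)^5], and the expected number in 24 is 24p.

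| p, opening rule | P(≥2 of 6) | Expected in 24 | p, list (half) | P(≥2 of 6) | Expected in 24 |
|---|---|---|---|---|---|
| 5% | 3.3% | 1.2 | 2.5% | 0.9% | 0.6 |
| 10% | 11.4% | 2.4 | 5% | 3.3% | 1.2 |
| 13.7% | 19.3% | 3.3 | 6.9% | 5.9% | 1.7 |

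For the one-third rule, start from 0 or 1 DLT in the first 6, add patients 7 to 24 one at a time, and stop when DLTs/n reaches 1/3. The probability of passing the first 6 and stopping later, under the opening rule, is 0.2%, 1.6% and 3.7% for the three rows.

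**The case against.** The best defence is that the opening sentence sets the frame, including the 6-week window that most entries omit, and that the list specifies it. That is an ordinary way to read a general statement followed by particulars, and it keeps every time limit working. It is probably what was intended, but the text does not say so, and the electrolyte exclusion makes most sense under the broad rule.

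Several narrowing points stand.
- A reader might infer that every short Grade 3 event is affected. It is not: colitis, neurotoxicity, neuromotor syndromes and pneumonitis are DLTs under both rules, and the listed exclusions are DLTs under neither.
- A reader might infer that the transaminase entries count only high or lasting values. They also count values above 3 x ULN with INR above 1.5 or symptoms, at any duration.
- The 75% entry catches some brief events. Two lost Vicineum doses leave 4/6 = 67% if doses are counted per drug, although 6/8 = 75% if they are pooled.
- A reader might infer that the exclusions are idle if the list governs. The infusion-reaction exclusion is not: Section 3.2.1.2 discontinues study drug for a Grade 3 reaction, so one in week 2 leaves at most 1 of 2 durvalumab doses and could otherwise trigger the 75% entry.
- Sections 3.3.2 and 3.6.1 are compatible once DLT status is known. Their difference matters only because status is unclear.

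It is also fair that Section 10.1 names the fraction of patients with adverse events as the primary endpoint and that all toxicities are tabulated, so a brief Grade 3 event will be visible either way. Its DLT label, and what follows from it, will not be settled by that table.

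**Conclusion.** The contradiction is real but bounded. It affects brief, treatment-related Grade 3 events that are in no named category, on no exclusion, and leave dosing at 75% or more. For those, Section 3.1.1 gives two answers, and one patient is enough to move 1 of 6 to 2 of 6.

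The table above is illustrative only. It uses all-follow-up single-agent rates as a ceiling for a 6-week window, an inferred denominator and an assumed half. It also leaves out DLTs below Grade 3 and those from the 75% entry, so the halved column does not estimate the list-based rate. Within those limits, the rules differ by about 0.6 to 1.6 patients in 24, and a later breach of the one-third rule stays unlikely.

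A reader might infer that the run-in decision or dose was wrong. The documents do not support that. Section 1.2.3 reports 12-week response in 12 patients, so the run-in appears to be over, and Section 3.1.2 let that decision weigh all available safety data. The same section describes most related events as Grade 3 or lower, which does not exclude Grade 3 events but gives neither their number nor their timing. No misclassified patient is shown. What is open is the DLT table, the MTD statement, the cumulative rule and the handling of any later patient. The plan should be corrected, because the remedy is cheap and removes a discretionary choice from the main safety result.

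**What to change.** 1. **Let the list govern.** Replace the opening sentence of Section 3.1.1 with wording such as: *A DLT is any event on the list below that occurs in the first 6 weeks of treatment.* Keep the sentence that removes toxicity with another clear cause. Hold-and-resume in Section 3.3.2 then works inside the window for Grade 3 events that are not DLTs.
2. **If the sponsor intends the broad rule instead,** delete the 3-day, 14-day and 2-week limits from the list, and add to Section 3.3.2 that resumption does not apply to a Grade 3 DLT in the window. The choice is clinical and belongs to the sponsor.
3. **State which rule was used** for the run-in decision.
4. **Report the DLT count per dose level under both rules** as a sensitivity check beside the MTD, because both rules stood while patients were being treated.

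The cost is one sentence in Section 3.1.1 (for the broad rule, also the deletions and one line in Section 3.3.2), one statement about the run-in and one extra column in the DLT table. Section 8.2 already collects severity, onset and resolution dates. A change of grade within an event, needed for the 3-day limit, may have to be read from source records.
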